5.8 Subject Withdrawal/Discontinuation Criteria

Subjects may withdraw consent at any time for any reason or be dropped from the trial at the discretion of the investigator should any untoward effect occur. In addition, a subject may be withdrawn by the investigator or the Sponsor if enrollment into the trial is inappropriate, the trial plan is violated, or for administrative and/or other safety reasons. Specific details regarding discontinuation or withdrawal procedures; including specific details regarding withdrawal from Future Biomedical Research, are provided in Section 7.1.4 – Other Procedures.

A subject must be discontinued from the trial for any of the following reasons:

- The subject or legal representative (such as a parent or legal guardian) withdraws consent.

A subject must be discontinued from treatment (but may continue to be monitored in the trial) for any of the following reasons:

- The subject or legal representative (such as a parent or legal guardian) withdraws consent for treatment but agrees to continue to participate in the regularly scheduled study activities.
- Documented disease progression as assessed by the investigator. (i.e., 2 consecutive assessments are needed for disease progression. Clinical deterioration will not be considered progression). Note: Subjects with documented disease progression may continue to receive trial treatment, at the discretion of the study investigator prior consultation with the Sponsor, if they meet the criteria outlined in Section 7.1.2.8.6.
- Unacceptable adverse experiences as described in Sections 5.2.1.2 and 5.6.1.
- Intercurrent illness that prevents further administration of treatment.

- The subject has a confirmed positive serum pregnancy test.
- Subjects who receive any non-protocol specified anti-myeloma therapy prior to documented progression will be discontinued from all study treatment (including lenalidomide and low dose dexamethasone); however, tumor assessments must continue at 4 week intervals until documented progression.
- Noncompliance with trial treatment or procedure requirements.
 - Subjects experiencing a > 12 weeks delay between pembrolizumab doses in the investigational arm (Arm A) or > 28 day delay for both lenalidomide and low dose dexamethasone in the control arm (Arm B) due to an adverse event(s) related to study treatment must be discontinued from treatment.

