 - Subjects experiencing >28 days delays in all study drugs due medical/surgical events or logistical reasons unrelated to study therapy must be discontinued from treatment.

NOTE: For both groups, if either pembrolizumab, lenalidomide or low-dose dexamethasone is discontinued due to unacceptable toxicity, subjects can continue to receive study treatment with the remaining study drugs without discontinuing from study.

- The subject is lost to follow-up.
- Administrative reasons.

The End of Treatment and Follow-up visit procedures are listed in Section 6 (Flow Chart) and Section 7.1.5 (Visit Requirements). After the end of treatment, each subject will be followed for 30 days for AE monitoring (SAEs will be collected for 90 days after the end of treatment as described in Section 7.2.3.1). Subjects who discontinue for reasons other than progressive disease will have post-treatment follow-up for disease status until disease progression, initiating a non-study cancer treatment, withdrawing consent or becoming lost to follow-up. Prior to discontinuing patients from therapy, consult with Sponsor and submit the Treatment Termination & Disease Assessment Termination Form. After documented disease progression or the start of new antineoplastic therapy, each subject will be followed for overall survival until death, withdrawal of consent, or the end of the study, whichever occurs first.

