6.0 TRIAL FLOW CHART

6.1 Trial Flow Chart

Trial Period:	Screening Phase	Treatment Cycles						End of Treatment		Post-treatment		
		Cycles 1-3 to be repeated beyond 3 cycles										
Treatment Cycle/Title: (28 days cycles)	Screening (Visit 1)	Cycle 1		Cycle 2		Cycle 3		Discon ^o	Post-Treatment Safety Follow-up	Efficacy Follow-up Visits	Survival Follow-up	
Cycle Day (visit day) (± 3 days after C1D1 unless otherwise specified)	(-28 to -1 days)	1 (+ 3 days)	22	1	15	1	8	At time of Discon	30 days post Discon	Every 4 weeks post Discon (± 7 days)	Every 12 weeks (± 7 days) or as directed by the Sponsor	
Administrative Procedures												
Informed Consent	X											
Informed Consent for Future Biomedical Research	X											
Inclusion/Exclusion Criteria	X											
Subject Identification Card	X											
Demographics and Medical History	X											
International Staging System (ISS)	X											
Prior and Concomitant Medication Review ^d	X	X	X	X	X	X	X	X	X			
Register REVLIMID REMS™ program (US ONLY) or country specific risk mitigation program	X											
Pregnancy Prevention Counseling ^l	X	X		X		X						
Obtain randomization number and study drug assignment using IVRS/IWRS	X											
Pembrolizumab Administration		See Section 6.1.1										
Lenalidomide Administration												
Dexamethasone Administration												
Post-study anticancer therapy status								X	X	X		
Survival Status ^p		↔							↔		X	
Clinical Procedures/Assessments												
Review Adverse Events ^d	X	X	X	X	X	X	X	X	X	X		
Full Physical Examination	X	X		X		X		X				
Directed Physical Examination (Arm A only)			X		X		X					
Vital Signs and Weight ^{a,d}	X	X	X	X	X	X	X	X				

Trial Period:	Screening Phase	Treatment Cycles						End of Treatment		Post-treatment	
		Cycles 1-3 to be repeated beyond 3 cycles									
Treatment Cycle/Title: (28 days cycles)	Screening (Visit 1)	Cycle 1		Cycle 2		Cycle 3		Discon ^o	Post-Treatment Safety Follow-up	Efficacy Follow-up Visits	Survival Follow-up
Cycle Day (visit day) (± 3 days after C1D1 unless otherwise specified)	(-28 to -1 days)	1 (+ 3 days)	22	1	15	1	8	At time of Discon	30 days post Discon	Every 4 weeks post Discon (± 7 days)	Every 12 weeks (± 7 days) or as directed by the Sponsor
12-Lead Electrocardiogram	X										
ECOG Performance Status	X	X		X		X		X			
Skeletal survey	X										
MRI or CT or PET/CT for extramedullary soft tissue plasmacytoma	X										
Disease Response Assessment by IMWG 2011 criteria [1] ⁿ		X ⁿ		X		X		X	X	X	

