7.1.2.8.5 Disease Assessment During Trial

For all patients, the central laboratory vendor will receive serum and urine samples from the sites on day 1 of every 28-day cycle for myeloma laboratory central testing during the trial. For urine myeloma laboratory testing, 24-hour urine collection is mandatory for all patients enrolled in the study.

Myeloma disease assessments should be performed by the investigator every 28 days and will be based on the IMWG criteria. There is a ± 3 day window for assessments performed after Day 1. Disease assessments should not be delayed because of delays in the start of treatment cycles.

Disease assessments should continue to be performed until documented disease progression, the start of new anti-cancer treatment, withdrawal of consent, death, or the end of the study, whichever occurs first. Two consecutive results from myeloma laboratory tests are needed to confirm biochemical-based disease progression. Subjects who have disease progression may continue on treatment if they meet the criteria for treatment beyond disease progression defined in Section 7.1.2.8.6.

Prior to discontinuing patients from therapy, consult with Sponsor and submit the Treatment Termination & Disease Assessment Termination Form.

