7.1.5.5.1 Survival Follow-up

Once a subject experiences confirmed disease progression or starts a new anti-myeloma therapy, the subject moves into the survival follow-up phase and should be contacted approximately every 12 weeks for at least 12 months following their discontinuation visit for assessment of survival status until death, withdrawal of consent, or the end of the study, whichever occurs first.

Survival status data may be requested more frequently than every 12 weeks. The Sponsor may request these additional data at time points such as prior to data cleaning, an external Data Monitoring Committee (eDMC) safety review, and/or efficacy interim analyses. All subjects who are in the Survival Follow-Up Phase and not known to have died prior to the request for these additional survival data will be contacted at that time.

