8.4 Analysis Endpoints

8.4.1 Efficacy Endpoints

Primary

Progression-free survival (PFS) – the International Myeloma Working Group response criteria (IMWG 2011) by **CAC blinded central review**

PFS is defined as the time from randomization to the first documented disease progression per IMWG 2011 based on CAC blinded central review or death due to any cause, whichever occurs first. See Section 8.6.1 for definition of censoring.

Secondary

Overall Survival (OS) OS is defined as the time from randomization to death due to any cause. Subjects without documented death at the time of the final analysis will be censored at the date of the last follow-up.

Overall Response Rate (ORR) – the International Myeloma Working Group response criteria (IMWG 2011 criteria) for partial, or better, responses by **CAC blinded central review**.

ORR is defined as the proportion of the subjects in the analysis population who achieved at least a partial response (CR+VGPR+PR) according to the IMWG 2011.

Duration of Response (DOR) – the International Myeloma Working Group response criteria (IMWG 2011) by **CAC blinded central review**.

For subjects who demonstrated at least a partial response, response duration is defined as the time from first documented evidence of at least a partial response until disease progression or death. Response duration for subjects who have not progressed or died at the time of analysis will be censored at the date of their last assessment.

Disease Control Rate (DCR) - the International Myeloma Working Group response criteria (IMWG 2011) for at least a partial response by **CAC blinded central review**.

Disease control rate is defined as the percentage of subjects who have achieved confirmed CR, VGPR, PR, or have demonstrated SD for at least 12 weeks prior to any evidence of progression.

Second Progression Free Survival (PFS2) - the time from randomization to subsequent disease progression after initiation of new anti-cancer therapy, or death from any cause, whichever occurs first, **by investigator assessment**.

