The stratified Miettinen and Nurminen's method based on sample size weighting will be used for comparison of the ORR between the treatment groups. A 95% confidence interval for the difference in response rates between the active arms and the standard therapy arm will be provided. Age and ISS stage will be used as the stratification factors in the analysis.

Duration of Response (DOR)

Response duration will be summarized descriptively using Kaplan-Meier medians and quartiles, results permitting. Only the subset of subjects who achieve at least a partial response will be included in this analysis.

Disease Control Rate (DCR)

The stratified Miettinen and Nurminen's method based on sample size weighting will be used for comparison of the DCR between the treatment groups. A 95% confidence interval for the difference in DC rates between the active arms and the standard therapy arm will be provided. Age and ISS stage will be used as the stratification factors in the analysis.

Second Progression-free Survival (PFS2)

The non-parametric Kaplan-Meier method will be used to estimate the PFS2 curves. The treatment difference in PFS2 will be assessed by the stratified log-rank test. A stratified Cox proportional hazards model with Efron's method of tie handling will be used to assess the magnitude of the treatment difference (i.e., the hazard ratio). The hazard ratio and its 95% confidence interval from the stratified Cox model with a single treatment covariate will be reported. Age and ISS stage will be used as the stratification factors in both the stratified log-rank test and the stratified Cox model.

Further details of PFS2 analyses will be described in supplemental SAP.

Table 16 summarizes the primary analysis approach for primary and secondary efficacy endpoints. Sensitivity analysis methods are described above for each endpoint.

Table 16 Analysis Strategy for Primary and Secondary Efficacy Endpoints

Endpoint/Variable (Description, Time Point)	Statistical Method†	Analysis Population	Missing Data Approach
Primary Endpoint			
PFS per IMWG 2011 by CAC blinded central review	Testing: Stratified Log-rank test. Estimation: Stratified Cox model with Efron's tie handling method	ITT	
 • Primary censoring rule • Sensitivity analysis 1 • Sensitivity analysis 2 (details in Table 15)
Secondary endpoints			

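### PFS2 is tested as a secondary endpoint, but no progression date on later therapy is scheduled after first PD; rules for subjects who switch therapy before PD also conflict, which touches primary PFS

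*Combined protocol and SAP*

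**What the plan says.** **Endpoint.** Section 3.2 lists PFS2 by investigator assessment among the secondary objectives. Section 8.4.1 defines it as "the time from randomization to subsequent disease progression after initiation of new anti-cancer therapy, or death from any cause", whichever is first. Section 8.6.1 states: "The treatment difference in PFS2 will be assessed by the stratified log-rank test". It adds a stratified Cox hazard ratio and leaves further detail to the supplemental SAP (sSAP).

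**When disease assessment ends.** Under Section 7.1.2.8.5, assessments run "until documented disease progression, the start of new anti-cancer treatment, withdrawal of consent", death or study end. Section 7.1.5.5 stops efficacy follow-up at the same points.

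**What follows.** Section 5.8: "After documented disease progression or the start of new antineoplastic therapy, each subject will be followed for overall survival until death". Section 7.1.5.5.1: the subject "should be contacted approximately every 12 weeks for at least 12 months following their discontinuation visit for assessment of survival status". Note p to the flow chart (Section 6.1) describes the same contact, again for survival status. In the flow chart as extracted, disease response and "Post-study anticancer therapy status" are marked up to the efficacy follow-up visits but not in the survival column.

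**Switching before PD.** The discontinuation list in Section 5.8 says that for subjects given non-protocol anti-myeloma therapy before progression, "tumor assessments must continue at 4 week intervals until documented progression". The closing paragraph of the same section gives subjects who stop for reasons other than PD "post-treatment follow-up for disease status until disease progression, initiating a non-study cancer treatment, withdrawing consent or becoming lost to follow-up".

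**The concern.** An endpoint that needs a progression on the next line of therapy needs someone to record that progression. Here the schedule stops looking for progression just when the PFS2 clock begins to depend on it. For a subject whose first PD occurs on study, death is the only PFS2 event the protocol provides for. A hazard ratio labelled PFS2 would then say little about outcome on subsequent therapy beyond what OS already says, and a reader could take it for independent evidence.

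The rules for subjects who switch before PD raise a second problem. If some were assessed to progression and others released to survival contacts, non-fatal events would come from a selected group in an open-label trial. The same choice decides whether such a subject can contribute a progression event to primary PFS.

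**Working it through.** **1. After first PD**

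| Needed for a non-fatal PFS2 event | What the protocol provides |
|---|---|
| Start of new therapy | Collected (Sections 7.1.1.5.4 and 7.1.5.5) |
| Disease assessment on that therapy | Stopped at first PD (Sections 7.1.2.8.5 and 7.1.5.5) |
| Progression date on that therapy | Not scheduled; contacts are for survival status (Sections 5.8, 7.1.5.5.1, flow chart note p) |
| Death date | Collected |

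Only the fatal component has a planned source.

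**2. Non-protocol therapy before PD**

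| Rule | Where |
|---|---|
| Continue 4-weekly assessment to progression | Section 5.8, discontinuation list |
| End assessment or active follow-up, or move to survival follow-up | Section 5.8, closing paragraph; Sections 5.5.2, 7.1.1.5.4, 7.1.2.8.5, 7.1.5.5, 7.1.5.5.1 |

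Two consequences follow.

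- *PFS2.* Under the first rule a non-fatal event could be recorded, provided that a first progression occurring on new therapy counts as the subsequent progression in Section 8.4.1. The wording does not settle this. Under the second rule it could not.
- *Primary PFS.* In the primary analysis in Table 15, a switcher with no PD and no death is censored at the last assessment before the new therapy. A documented PD is an event, with no exclusion for PD after new therapy. The first rule can therefore produce an event where the second produces a censored time.

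**3. Size of the group at risk (illustration only)**

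Inputs from Section 8.9: 640 subjects 1:1, 18-month enrolment, exponential PFS with control median 25.5 months, exponential OS with 70% alive at 36 months in control, dropout 5% at 4 years, and target hazard ratios 0.65 (PFS) and 0.70 (OS). Assumed here: uniform enrolment, all 640 entered, exponential dropout.

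Monthly hazards:
- PFS: control ln 2/25.5 = 0.02718; pembrolizumab × 0.65 = 0.01767
- OS: control −ln 0.70/36 = 0.00991; pembrolizumab × 0.70 = 0.00694
- Dropout: d = −ln 0.95/48 = 0.00107

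Expected events per arm at month T are 320 × the average, over follow-up f uniform on (T − 18, T), of λ/(λ + d) × [1 − exp(−(λ + d)f)]. Every death is also a PFS event, so alive after first progression = PFS events − deaths.

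Check against the plan: the model gives 233 PFS events at month 30 (plan about 227). At month 20 it gives 135, against about 115 in Table 18. It therefore runs ahead of the plan early on, and the counts below may be somewhat high.

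| Month | PFS events | Deaths | Alive after first progression |
|---|---|---|---|
| 18 | 112 | 46 | 66 |
| 20 | 135 | 56 | 79 |
| 23 | 98 + 69 = 167 | 41 + 29 = 70 | 97 (58 control, 39 pembrolizumab) |

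Month 23 is an upper limit for time on study at the hold: from the original protocol (28-JUL-2015) to the hold (03-JUL-2017) is 706 days, and 706/30.44 = 23.2 months. The date of first enrolment is not given. With both hazard ratios at 1, the month-23 figure is 115. Using the SAP's other dropout figure (2% at one year) leaves it at 97 after rounding.

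**The case against.** **The details are deferred.** Section 8.6.1 leaves PFS2 to the sSAP, and the CRF may have asked for second-progression dates. A reader might infer from the protocol that none were collected; the documents do not support that, because neither the CRF nor the sSAP is among them. But an sSAP can set censoring rules only for data that exist, and the protocol schedules none. The request in Section 7.1.5.5 for every effort to obtain response data applies to a follow-up period that the same section ends at PD or new therapy.

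**The endpoint is nominal.** This stands. Section 8.8 carries alpha only from PFS to OS, and Section 8.6.1 calls other p-values nominal. The absence of second-progression dates does not affect the error rate. It does not follow that PFS is untouched by the separate conflict over switchers, for the Table 15 reason given above.

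**The conflict is narrower than it looks.** This also stands. The 4-weekly rule sits in a list of reasons for stopping study treatment, so it most naturally covers subjects still on treatment who receive outside therapy. A reader might infer that, because the 2017 hold took everyone off treatment, the conflict reaches nearly all subjects without PD. The text does not support this: Section 2.1 sends hold subjects to long-term safety and survival follow-up, and the Document History for amendment 08 has all remaining participants in survival follow-up. Neither points to the 4-weekly rule.

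**The counts are not missing events.** Correct. They show how many subjects could be affected. No share of unrecorded second progressions can be derived from the documents.

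**Conclusion.** The point holds. Followed as written, the protocol gives PFS2 no scheduled non-fatal event for subjects with first PD, so the tested hazard ratio would largely restate OS. On design assumptions the group concerned is about 66 to 97 of 640 subjects at months 18 to 23. This rests on full and uniform enrolment and on the planned hazard ratios; actual counts are not given.

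The contradiction over subjects who receive non-protocol therapy before PD is real but probably confined to those still on study treatment. Its size cannot be estimated. It matters for non-fatal PFS2 events, if a first progression on new therapy counts, and for primary PFS censoring. PFS2's nominal status limits the harm from the first problem to misreading of a secondary result. The sponsor should act on both, mainly in reporting.

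**What to change.** 1. Unless second-progression dates were collected systematically, withdraw the PFS2 test or report PFS2 descriptively. Show fatal and non-fatal events by arm, and state that second progression after first PD was not scheduled for collection. Cost: text in the sSAP or CSR. Section 8.0 already allows modified analyses to be reported in the CSR.
2. If survival contacts are still open, add to the existing 12-weekly contact the investigator-reported progression date on the first subsequent therapy, with that therapy's start date. Cost: one CRF item and no new visits. This may be moot under amendment 08, which ends data collection after the final database lock.
3. Reconcile the 4-weekly rule in Section 5.8 with that section's closing paragraph and with Sections 5.5.2, 7.1.1.5.4, 7.1.2.8.5, 7.1.5.5 and 7.1.5.5.1. State in the CSR which rule was applied to subjects who switched before PD, and its effect on primary PFS censoring. Cost: text, plus a listing of the subjects concerned.

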7.1.5.5.2 Follow-up Post-Allogeneic Stem Cell Transplantation

In the event a subject receives an allo-SCT within 24 months of the last dose of pembrolizumab or before the end of the study, the following events will be collected as ECIs (see Section 7.2.3.2) through 18 months from the date of allo-SCT: GVHD, febrile syndrome treated with steroids, pulmonary complications, hepatic veno-occlusive disease and/or sinusoidal syndrome, immune-mediated AEs, critical illness, and transplant-related mortality. If available and relevant to an event post allo-SCT, concomitant medications and/or laboratory results may be reported. Additional medically important AEs may be submitted at the investigator's discretion. Post-allogeneic SCT ECIs that occur after the normal safety follow-up period must be assessed for seriousness and causality and reported to the Sponsor as follows: within 24 hours if serious regardless of causality, or if non-serious and considered to be drug-related; and 5 calendar days if non-serious and not considered to be drug-related.

7.1.5.6 Survival Status

To ensure current and complete survival data is available at the time of database locks, updated survival status may be requested during the course of the study by the Sponsor. For example, updated survival status may be requested prior to but not limited to an external Data Monitoring Committee (eDMC) review, interim and/or final analysis. Upon Sponsor notification, all subjects who do not/will not have a scheduled study visit or study contact during the Sponsor-defined time period will be contacted for their survival status (excluding subjects who have previously recorded a death event in the collection tool).

